5.5. Concomitant Medications

All subjects will be questioned about concomitant medication use at each study visit. In addition the following concomitant medications that the subject had been taking from the study they enrolled from (ie, Study A3921096, Study A3921094 or Study A3921095) and will continue to take in this study will be recorded:

Table 2. Concomitant Medications

| Treatment Type | Information Recorded | Recording Period |
|---------------------------------|--|--------------------------------------|
| Ulcerative colitis (UC)* | Daily dose, unit, frequency, route, start and stop dates | Treatment period Follow-up period |
| Oral corticosteroids | Total daily dose, reason for dose change, start and stop dates | Treatment period Follow-up period |
| Lipid lowering agents | Daily dose, unit, frequency, route, start and stop dates | Treatment period Follow-up period |
| Anti-hypertension agents | Start and stop dates | Treatment period Follow-up period |
| Anti-diabetic agents | Start and stop dates | Treatment period Follow-up period |
| All other treatments+ | Indication, start and stop dates | Treatment period Follow-up period |

* Concomitant treatment for UC must remain at a stable dose (no increase or decrease) during the study treatment period, with the exception of oral 5-ASA or sulfasalazine and oral corticosteroids as described below.

+ Includes nonprescription drugs, vitamins, and dietary supplements.

The following therapies for the treatment of UC are allowed providing their doses are not changed (reduced or increased), with the exception of oral 5-ASA or sulfasalazine and oral corticosteroids (see below) during the study treatment period:

- Oral 5-ASA or sulfasalazine dose modifications during the study are permitted.
- Chronic treatment for ulcerative colitis with antibiotics (eg, metronidazole, rifaximin) if continued from the preceding study.

Oral Corticosteroids

- Oral corticosteroids are allowed for subjects entering Study A3921139 on oral corticosteroids (maximum dose of 25 mg/day of oral prednisone or equivalent) and tapering must commence starting the first week of the study.
- The daily dose of oral prednisone or equivalent should be decreased at a rate of 5 mg per week until the dose reaches 20 mg/day, then reduce by 2.5 mg to 5.0 mg weekly until the dose reaches 0 mg.

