5.7. Rescue Therapy

If a subject requires initiation of a new therapy for UC (including re-initiation of oral corticosteroid therapy above 10 mg/day of prednisone or equivalent after a subject has achieved steroid-free status during either Study A3921096 or A3921139), the subject should be withdrawn from the study and appropriate agents should be given at the discretion of the investigator. If a subject discontinues the use of background oral 5-ASA or sulfasalazine during the study and/or has the therapy re-initiated, this will not constitute rescue therapy, and the subject will be permitted to remain in the study.

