6.3. Subject Withdrawal

Should a subject withdraw from active treatment, the subject should complete the procedures listed at the Month 12/ET Visit. After completing the procedures for the early withdrawal visit, the subject should return for a safety evaluation to occur approximately 4 weeks after discontinuing study medication as per the follow-up visit.

Subjects will be withdrawn from the study if any of the following occurs during the study treatment period:

- If a subject who enrolled from the induction studies A3921094 or A3921095 (ie, non-responders) fails to demonstrate clinical response at Month 2. Clinical response is defined by a decrease from the induction study baseline (A3921094 or A3921095) Mayo score of at least 3 points and at least 30%, with an accompanying decrease in the rectal bleeding subscore of at least 1 point or an absolute rectal bleeding subscore of 0 or 1. The endoscopic subscore based on central reading will be used to assess clinical response.
- If rescue therapy is initiated for UC with the exception of oral 5-ASA or sulfasalazine. Rescue therapy includes re-initiation of oral corticosteroid therapy above 10 mg/day of prednisone or equivalent after a subject has achieved steroid-free status during either Study A3921096 or A3921139.
- If a subject undergoes surgery for UC.
- If a subject remains on oral corticosteroids exceeding 15 mg/day of prednisone or equivalent after Month 3.

A subject may be withdrawn from the study for any of the safety concerns as listed in [Appendix 3](#).

Subjects who develop a serious infection during the study, defined as any infection (viral, bacterial, and fungal) requiring hospitalization or parenteral antimicrobials or being classified as a serious adverse event should be withdrawn from the study (see [Section 7.3.10](#)).

All abnormal laboratory events of clinical significance should be followed until the laboratory values have returned to normal or baseline levels (see [Appendix 3](#)). Subjects who meet the discontinuation criteria described in [Appendix 3](#) will be withdrawn from the study.

If a subject has any clinically significant, study-related abnormalities at the conclusion of the study, the Pfizer medical monitor (or designated representative) should be notified and every effort should be made to arrange follow-up evaluations at appropriate intervals to document the course of the abnormalities.

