Appendix 3. Guidelines for Monitoring and Discontinuations

The following laboratory abnormalities require monitoring and re-testing ideally within 3-5 days:

- Absolute neutrophil count $<1.2 \times 10^9/L$ ($<1200/mm^3$).
- Absolute lymphocyte count $<0.5 \times 10^9/L$ ($<500/mm^3$).
- Any single hemoglobin value <8.0 g/dL, or any decrease in hemoglobin >2.0 g/dL from baseline.
- Platelet count $<100 \times 10^9/L$ ($<100,000/mm^3$).
- An increase in serum creatinine of $>50\%$ from the baseline value; OR an absolute increase in serum creatinine >0.5 mg/dL (>44.2 umol/L) from baseline value.
- Any single AST and/or ALT elevation ≥ 3 times the upper limit of normal (repeat laboratory testing should include albumin, creatine kinase, total bilirubin, direct and indirect bilirubin, GGT, PT [prothrombin time] with INR [international normalized ratio], and alkaline phosphatase), regardless of the total bilirubin. (Please note that 3 times the upper limit of normal increases in ALT, AST need confirmation on separate blood draw before undertaking thorough evaluation for liver injury).
- Any creatine kinase (CK) >10 times the upper limit of normal (repeat laboratory testing should also include cardiac troponin).
- For women of child-bearing potential with any positive urine β -hCG test, the subject will have study drug interrupted and a serum sample submitted to the central laboratory for β -hCG testing.

Additional individual subject safety monitoring in addition to these guidelines is at the discretion of the investigator and dependent on any perceived safety concerns. Unscheduled laboratory testing through the central laboratory may be obtained at any time during the study to assess such concerns, and a subject may be withdrawn at any time at the discretion of the investigator.

Treatment with tofacitinib will be discontinued and the subject withdrawn from this study for:

- Serious infections defined as any infection (viral, bacterial, and fungal) requiring parenteral antimicrobial therapy, hospitalization for treatment, or meeting other criteria that require the infection to be classified as serious adverse event.

- Two sequential absolute neutrophil counts $<0.75 \times 10^9/L$ ($<750/mm^3$).

- Two sequential absolute lymphocyte counts $<0.5 \times 10^9/L$ ($<500/mm^3$).
- Two sequential hemoglobin <8.0 g/dL or a decrease of $>30\%$ from baseline.
- Two sequential platelet counts $<75 \times 10^9/L$ ($<75,000/mm^3$).

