- Two sequential increases in serum creatinine $>50\%$ over the baseline value AND an absolute increase in serum creatinine >0.5 mg/dL (>44.2 umol/L).
- Two sequential AST or ALT elevation ≥ 3 times the upper limit of normal with at least one total bilirubin value ≥ 2 times the upper limit of normal.^a
- Two sequential AST or ALT elevation ≥ 3 times the upper limit of normal accompanied by signs or symptoms consistent with hepatic injury.^a
- Two sequential AST or ALT elevation ≥ 5 times the upper limit of normal, regardless of total bilirubin or accompanying signs or symptoms.^a
- Two sequential CK elevations >10 times the upper limit of normal, unless the causality is known not to be medically serious (eg, exercise induced).
- Female subjects found to be pregnant during the study.
- Initiation of a new treatment for UC.
- Surgery for UC.
- Other serious or severe AEs, after consultation with the Pfizer medical monitor or designee.

C
C
I

- a In each case, there is a need for additional investigations, such as review of ethanol, recreational drug and dietary supplement consumption; testing for acute hepatitis A, B or C infection and biliary tract imaging should be promptly discussed with the Pfizer medical monitor or designee.

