7. HANDLING OF MISSING VALUES

7.1. Efficacy Endpoints

For binary efficacy endpoints (Remission, Clinical remission, Mucosal healing, PMS remission, Clinical response) derived from Mayo subscores (site-read endoscopic subscore was used), data will be summarized based on the observed-case data and non-responder imputation and last observation carried forward imputation (NRI-LOCF). The NRI-LOCF approach is described as the following:

- For subjects who discontinued from the study, other than those who moved to Study A3921288 or to the Japan post-marketing surveillance study, or due to regulatory approval in Japan, NRI will be used for missing data up to the visit (using the lower bound of visit window as defined in [Appendix 1](#)) they would have reached if they had stayed at the study. The missing data before time of discontinuation will be imputed as non-responders.
- For ongoing subjects (for interim analyses only), they will be included in the summary tables only up to visits with non-missing data in the dataset for the interim report. For subjects with intermittent missing data, they will be treated as non-responders. Otherwise no imputation for missing data will be applied since it's hard to separate the true missing data from being late for the scheduled visit.
- For completed subjects, they will be included in the summary tables only up to the completion visit. Missing data before the completion will be imputed using the NRI approach.
- For subjects who discontinued from the study and moved to Study A3921288 or to the Japan post-marketing surveillance study, or due to regulatory approval in Japan, LOCF will be used up to the visit (using the lower bound of visit window as defined in [Appendix 1](#)) they would have reached if they had stayed in the study. The missing data before time of discontinuation will be imputed as non-responders. This approach will likely overestimate the proportions of subjects who achieve the binary endpoints since it is assumed that the response status remains after subjects moved to Study A3921288 or the Japan post-marketing surveillance study.

For continuous endpoints total Mayo score and Partial Mayo score, data will be summarized based on the observed-case data and LOCF. The LOCF approach is described as the following:

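### Protocol passages disagree on whether a first-time start of oral 5-ASA or sulfasalazine leads to withdrawal, so remission summaries and exposure time can depend on the passage a site follows

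*Protocol*

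**What the plan says.** Four places in the Protocol bear on a subject who begins oral 5-ASA or sulfasalazine during the study.

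- **Section 6.3** lists rescue therapy as a reason for withdrawal, worded "If rescue therapy is initiated for UC with the exception of oral 5-ASA or sulfasalazine". The exception carries no limit to background or resumed therapy. The same section also makes the appendix binding: "Subjects who meet the discontinuation criteria described in" Appendix 3 are to be withdrawn.
- **Section 5.7** sets its trigger as "If a subject requires initiation of a new therapy for UC". Its exemption is narrower: a subject who "discontinues the use of background oral 5-ASA or sulfasalazine during the study and/or has the therapy re-initiated, this will not constitute rescue therapy" and may stay. The Protocol Summary and Section 3 carry the same background-limited exemption.
- **Appendix 3** opens its stopping list with "Treatment with tofacitinib will be discontinued and the subject withdrawn from this study for" and includes "Initiation of a new treatment for UC". It names no exception.
- **Section 5.5** says "Oral 5-ASA or sulfasalazine dose modifications during the study are permitted". It does not address a first-time start.

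For binary Mayo-based endpoints, SAP Section 7.1 says "data will be summarized based on the observed-case data and non-responder imputation and last observation carried forward imputation (NRI-LOCF"). SAP Section 7.2 gives IBDQ remission the same handling.

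**The concern.** The event is plausible. A subject who entered without oral 5-ASA has worsening symptoms, and the site adds it. A site working from the rescue-therapy bullet in Section 6.3 would keep the subject on tofacitinib. A site working from Section 5.7 or Appendix 3 would withdraw the same subject.

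Two things are at stake. The first is long-term remission. A retained subject contributes scores obtained with added UC therapy, while a withdrawn one contributes imputed non-response or nothing, depending on the summary. The second is the primary objective, safety, because withdrawal shortens the observed exposure. The visible text of SAP Section 7.1 has no rule for UC therapy added by a retained subject. Part of that section is redacted, so such a rule may exist there.

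**Working it through.** No figure in the plan is in dispute here, so the check is a comparison of text, a trace through the SAP, and a sizing on stated assumptions.

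**1. Passages side by side**

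| Protocol passage | First-time start of oral 5-ASA or sulfasalazine | Re-start of a background drug |
|---|---|---|
| 6.3, rescue-therapy bullet | Exempt, subject stays | Exempt, subject stays |
| 5.7 (also Summary, Section 3) | Falls under new UC therapy; the exemption does not reach it, so withdrawn | Expressly exempt, subject stays |
| Appendix 3 (made mandatory by 6.3) | New UC treatment, no exception, so withdrawn | Not naturally a new treatment |
| 5.5 | Silent (covers dose modification) | Silent |

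Only the first-time start gets opposite dispositions. SAP Section 2.1 repeats the withdrawal for rescue therapy without defining it, so it does not settle the matter.

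**2. What withdrawal does in each summary (SAP Sections 7.1, 7.2 and 8.2.4)**

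- Binary endpoints (site-read Mayo-based, and IBDQ remission), NRI-LOCF: missing values become non-response through the last visit the subject could have reached.
- Binary endpoints, observed case: the subject leaves the denominator.
- Continuous Mayo and partial Mayo scores: observed case and LOCF, so the last value is carried forward.
- Central-read endpoints outside the induction non-responder subpopulation: observed data only.
- Incidence rates of adverse events of special interest: person-time ends at last dose + 28 days, or earlier at the first event or death. Deaths, malignancies and MACE with later onset are still counted as events.

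**3. Visits touched, by example**

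Take withdrawal just after Month 6, for a subject who could have been followed to Month 36.

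- PMS remission: Months 9 to 36 in 3-month steps, (36 − 9)/3 + 1 = 10 visits. At Months 12, 24 and 36 the schedule marks the full Mayo score, so PMS there comes from its components.
- Remission, clinical remission and mucosal healing: Months 12, 24 and 36, so 3 visits.
- Event-free person-time lost: 36 − 6 = 30 months (the 28 days are added in either case).

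**4. Size in the NRI-LOCF summary**

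Let *x* be the share of subjects affected and *p* the proportion of them who would have responded if retained. The documents give neither. Comparing all retained with all withdrawn, the NRI proportion falls by *x × p*.

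- Low end: 1% × 30% = 0.3 percentage points.
- Middle: 3% × 50% = 1.5 points.
- High end: 5% × 70% = 3.5 points.

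With the planned total of 460 + 440 = 900 subjects, 1% to 5% is 9 to 45 subjects.

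**5. Observed case, for comparison**

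Let 50% of all other subjects respond (assumed), with *x* = 5% and no other missing data.

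| *p* | All retained | Withdrawn, NRI | Withdrawn, observed case |
|---|---|---|---|
| 70% | 0.95 × 50% + 0.05 × 70% = 51.0% | 0.95 × 50% = 47.5% | 50.0% |
| 30% | 0.95 × 50% + 0.05 × 30% = 49.0% | 47.5% | 50.0% |

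The observed-case result moves by up to 1.0 point here, in either direction. Counting every first-time starter as a non-responder from the start date gives 47.5% in both rows, whichever disposition the site chose.

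**The case against.** The best defence is that the Section 6.3 bullet is shorthand. The background-limited exemption appears in the Summary, Section 3 and Section 5.7, so the bullet can be read as a short reference to it. No passage names first-time initiation, which makes the Section 5.7 side an inference from its general trigger and its limited exemption. Section 6.3 read as a whole also does not cleanly keep the subject in, because it imports the Appendix 3 list.

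This stands in part. The shorthand reading is possible, but the bullet neither says so nor cross-refers to Section 5.7. The Appendix 3 link does not remove the conflict; it places the conflict inside Section 6.3. That section also has a permissive sentence about Appendix 3 safety concerns, but the appendix lead-in is itself mandatory.

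Three stronger readings are tempting and are not supported:

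- *Re-starting a background drug is also in conflict with Appendix 3.* Resuming a background drug is not naturally a new treatment, and three passages expressly allow it.
- *There are three different rules.* On a first-time start, Section 5.7 and Appendix 3 agree. The conflict has two sides.
- *Withdrawal turns every later efficacy result into non-response.* That holds only for binary endpoints in the NRI-LOCF summary, only through the last visit the subject could have reached, and it changes a result only where a retained subject would have responded.

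It is also fair to say that the study is descriptive, with no hypothesis test and no primary efficacy endpoint, and that the number of such subjects may be zero. By Amendment 11 all subjects had passed Month 36, so new wording cannot alter conduct up to that visit.

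**Conclusion.** The inconsistency is real and nothing else in the documents resolves it. A first-time start of oral 5-ASA or sulfasalazine is exempt under the Section 6.3 bullet and leads to withdrawal under Section 5.7 and Appendix 3. The reading of the text is firm. The size of the consequence is not known, because the documents give no frequency of first-time starts.

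The 0.3 to 3.5 point range for NRI-LOCF proportions rests on two assumptions (1% to 5% affected, 30% to 70% of them responding if retained) and on the contrast between all retained and all withdrawn. Mixed site practice would give something smaller. Effects on observed-case results can go either way, and exposure time is affected as well. No view is taken on which clinical rule is right.

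**What to change.** 1. Reconcile Protocol Sections 5.5, 5.7 and 6.3 and Appendix 3 into one statement on whether first-time initiation of oral 5-ASA or sulfasalazine leads to withdrawal, and cross-refer to it from the other places. The clinical choice is the sponsor's.
2. From the recorded UC concomitant medication, list all first-time starters with start date, disposition and date of last dose. Section 5.5 has sites ask about concomitant medication at every visit, and Table 2 records start and stop dates for UC treatment. The lead-in to Table 2 speaks of drugs carried over from the parent study, so first confirm that newly begun drugs were captured in the same way.
3. If the list is not empty, add one supportive NRI-LOCF table for the binary endpoints that counts these subjects as non-responders from the start date, whatever their disposition. If it is empty, report that and the matter is closed.

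The listing and table cover visits through Month 36, which rewording can no longer reach. They do not restore lost safety follow-up, but the listing makes it visible. The cost is clarifying text, one listing and at most one extra table. Supportive remission rates may come out slightly lower.

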- *For example only*, if a subject is receiving oral prednisone 25 mg/day at baseline, the subject's corticosteroid tapering regimen could be as follows:
 - Baseline/Day 1: 25 mg/day
 - Week 1 (± 2 days): 20 mg/day
 - Week 2 (± 2 days): 15 mg/day
 - Week 3 (± 2 days): 10 mg/day
 - Week 4 (± 2 days): 7.5 mg/day
 - Week 5 (± 2 days): 5.0 mg/day
 - Week 6 (± 2 days): 2.5 mg/day
 - Week 7 (± 2 days): 0 mg/day
- Oral budesonide: the daily dose should be decreased at a rate of 3 mg every 3 weeks until discontinuation.
 - *For example only*, if a subject is receiving oral budesonide 9 mg/day at baseline, the subject's steroid tapering regimen could be as follows:
 - Week 1 – 3 (Day 1 – Day 21): 6 mg/day
 - Week 4 – 6 (Day 22 – Day 42): 3 mg/day
 - Week 7 and beyond (\geq Day 43): 0 mg/day
- If a subject experiences worsening of UC symptoms during the corticosteroid taper or symptoms related to chronic corticosteroid therapy that in the opinion of the investigator are attributable to the corticosteroid taper, then the investigator may instruct the subject to revert back to the preceding dose in the taper schedule (ie, "step up"). The signs or symptoms leading to this change (eg, increased stool frequency, increased rectal bleeding) must be recorded on the CRF. Study subjects with signs or

symptoms attributed to corticosteroid taper are permitted to step up their corticosteroid dosage one time during participation in A3921139 and then resume corticosteroid taper to achieve steroid-free status.

- If a subject cannot tolerate tapering their corticosteroid dose below 10 mg/day, the subject is permitted to remain in the study provided their dose does not exceed 10 mg/day. However, efforts should be made to taper corticosteroids completely off.
- Re-initiation of oral corticosteroid therapy above 10 mg/day of prednisone or equivalent for the treatment of UC, after a subject has achieved steroid-free status during either Study A3921096 or A3921139, will be considered rescue therapy and the subject should be discontinued from the study.
- Initiation of oral corticosteroids during Study A3921139 for the treatment of non-UC indications (eg, allergic reaction, asthma, etc) may be permitted and the sponsor should be notified.

Subjects receiving tofacitinib 10 mg BID and either concomitant combined hormonal contraceptives or hormone replacement therapy must have their tofacitinib dose reduced to 5 mg BID.

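### Protocol 5.5 and 6.3 give different answers for a subject who entered on oral corticosteroids, never came off them, and is above 10 and up to 15 mg/day after Month 3

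*Protocol*

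**What the plan says.** Protocol 5.5 allows oral corticosteroids for subjects who enter on them ("maximum dose of 25 mg/day of oral prednisone or equivalent") and sets the taper: the prednisone dose "should be decreased at a rate of 5 mg per week until the dose reaches 20 mg/day". From that level the weekly step is 2.5 to 5 mg, down to zero. One step-up to the preceding dose is allowed, after which the taper resumes. For a subject who cannot get below 10 mg/day, "the subject is permitted to remain in the study provided their dose does not exceed 10 mg/day". This condition has no time point.

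Protocol 6.3 opens its list with "Subjects will be withdrawn from the study if any of the following occurs during the study treatment period". One item reads "If a subject remains on oral corticosteroids exceeding 15 mg/day of prednisone or equivalent after Month 3".

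A separate rule covers steroids that are restarted. Section 5.5 treats as rescue "Re-initiation of oral corticosteroid therapy above 10 mg/day of prednisone or equivalent for the treatment of UC, after a subject has achieved steroid-free status". Section 5.7 counts as a new therapy "re-initiation of oral corticosteroid therapy above 10 mg/day of prednisone or equivalent", and 6.3 repeats the same 10 mg/day limit among its withdrawal grounds.

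The SAP mentions the taper in its description of the design (Section 2.1) but gives no dose limit.

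**The concern.** Both rules address a subject whose taper has not been completed, and they use different doses. Between the two limits a site following 5.5 would have reason to take the subject out, and a site following 6.3 would have none.

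The choice feeds into the analysis. The remission, clinical remission and mucosal healing definitions visible in SAP 6.1.2 do not require the subject to be off steroids. A subject kept on 12.5 mg/day can therefore be counted as a remitter, while the same subject, if withdrawn, is imputed as a non-responder in one of the two planned summaries. Safety follow-up is touched as well: for most events of special interest, SAP 8.2.4 ends time at risk 28 days after the last dose, so retention adds person-time under steroid exposure. The deviation list required by SAP 5.5 also needs an answer to whether such a subject is a deviation.

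**Working it through.** The plan gives no figure to reproduce, so the check compares the rules dose by dose, finds who can be in the gap, and follows such a subject into the analysis.

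**Inputs.** Limit for staying: 10 mg/day (Protocol 5.5). Withdrawal limit: above 15 mg/day after Month 3 (6.3). Entry maximum 25 mg/day; taper 5 mg per week down to 20 mg/day, then 2.5 to 5 mg per week to 0; one step-up (5.5). Month 3 is taken as Day 90, from the 30-day months in SAP Appendix 1: 90/7 = 12.9 weeks.

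**Step 1. The two rules after Month 3, for a subject never steroid-free.**

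| Dose (mg/day) | Protocol 5.5 | Protocol 6.3 | Agree? |
|---|---|---|---|
| 10 or less | may remain | no withdrawal | yes |
| above 10, up to and including 15 | condition not met | no withdrawal | **no** |
| above 15 | condition not met | withdrawal | yes |

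Exactly 10 mg/day is not in conflict; exactly 15 mg/day is. Before Month 3, 6.3 sets no limit for a subject still tapering.

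**Step 2. Can a subject following the prednisone taper be in the band after Month 3?** From 25 mg/day, the weeks needed to reach dose D are 1 (for 25 to 20) plus (20 − D)/r, where r is the weekly reduction.

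- Fastest, r = 5: 10 mg/day at 1 + 10/5 = week 3; 0 at 1 + 20/5 = week 5.
- Slowest, r = 2.5: 10 mg/day at 1 + 10/2.5 = week 5; 0 at 1 + 20/2.5 = week 9.
- Slowest with one step-up, assumed to add 2 weeks: at or below 10 mg/day for good by 5 + 2 = week 7 at the latest; 0 at 9 + 2 = week 11.

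All of these end before week 12.9. Section 5.5 does not say how long a step-up lasts. To leave a subject above 10 mg/day at Month 3, it would have to add more than 12.9 − 5 = 7.9 weeks. The band therefore holds only subjects whose taper failed or was not followed.

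**Step 3. Who is outside the conflict.**

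- Subjects who became steroid-free and restart above 10 mg/day for UC: 5.5, 5.7 and 6.3 give the same answer.
- Induction non-responders without clinical response at Month 2: 6.3 withdraws them before the Month 3 rule can apply.
- Subjects given steroids for a non-UC indication: 5.5 treats these separately.

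**Step 4. Consequence in the SAP 7.1 summaries, for a subject in the band.**

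| | Kept | Withdrawn |
|---|---|---|
| Binary, NRI-LOCF | own status at each visit | non-responder where data are missing, up to the visit the subject would have reached |
| Binary, observed case | own status at each visit | no data, so out of the summary |
| Continuous, LOCF | own score | last score carried forward |

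**The case against.** The strongest defence is a layered reading. Section 5.5 grants a permission and does not order withdrawal, whereas its next item, on restarting steroids, does call for discontinuation. The author could write an order where one was meant. On this reading a subject at 12.5 mg/day is outside the 5.5 allowance, and so a deviation, but has not reached the mandatory trigger in 6.3. This is a possible reading, and it stands that withdrawal under 5.5 follows only by implication. It does not settle the matter. The 5.5 condition is about remaining in the study, and the aim of getting off steroids altogether is stated separately. Nor can 15 mg/day be slack for a taper still on schedule, since Step 2 shows that taper is finished by Month 3. No text says that the layered reading is the one intended.

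Four stronger readings are tempting, and the documents do not support them.

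- A reader might infer that 5.7 conflicts with 6.3 too. It does not: 6.3 contains the same 10 mg/day rule for restarting.
- A reader might count all of the roughly 440 expected induction non-responders as exposed. Only those with a Month 2 response who are still on steroids can be.
- A reader might turn this into an effect, for example 9 of 900 subjects moving remission by 1 percentage point. That is only an upper bound. It requires every such subject to be a remitter if kept and withdrawn otherwise, and the documents give no count.
- A reader might say that withdrawal decides the efficacy result. Safety is the primary objective, efficacy is descriptive without testing, and NRI-LOCF stands beside an observed-case summary.

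It is also fair that a protocol change comes late. By Amendment 11 all subjects had passed Month 36, so its prospective effect is limited. The value that remains is in how the existing data are classified and reported.

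**Conclusion.** The contradiction is real and narrow. It concerns 5.5 against 6.3, for subjects who entered on oral corticosteroids, never became steroid-free, and are above 10 and up to and including 15 mg/day after Month 3. For them the text does not determine whether they stay, and their remission status under NRI depends on that decision.

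The size cannot be derived. It is probably small, because only failed or departed tapers reach the band and, among induction non-responders, only those with a Month 2 response. This rests on Month 3 being about Day 90, on a step-up adding about 2 weeks, and on the prednisone schedule. It is worth correcting because the conflicting rules decide who is withdrawn, and the check is cheap. The documents give no basis here for saying which limit is right.

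**What to change.** Reconcile Protocol 5.5 and 6.3 for this group and state which governs. Section 5.7 needs no change. The form of the rule and the limit are for the sponsor and its clinicians. The clarification should also say at which assessment the Month 3 condition is judged, since scheduled visits fall at Months 2 and 4.

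In the study report:

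- List the subjects who entered on oral corticosteroids, never became steroid-free, and were above 10 and up to 15 mg/day after Month 3, with dose, dates, and whether they stayed or were withdrawn. Table 2 of Protocol 5.5 already requires total daily oral corticosteroid dose, reasons for change, and dates. Flag courses given for non-UC indications.
- Repeat the NRI remission table with these subjects handled in one way, for example all as non-responders from the first day in the band. This is a sensitivity analysis and implies no choice of clinical rule. If the listing is empty, the table is not needed.

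Cost: one clarification, one listing and one sensitivity table, with no new data collection.
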